- The percentage of subjects with mRS 0-2 at 1 year, 3 years and 5 years

Additional Endpoints:

- The percentage of target aneurysm rupture up to 1 year, 3 years and 5 years
- No migration (defined as ≤ 2 mm) of the device at 1 year, 3 years and 5 years

Sample Size Justification

A meta-analysis was executed to determine the Performance Goal (PG) for the primary safety endpoint of a clinical study of the PulseRider®. Based on this meta-analysis, a rate of 9.9% rounded to 10% (95% CI: 5.9% - 16.1%) for death due to neurological causes or major ipsilateral stroke was calculated. A 5% margin of indifference for the primary safety endpoint is proposed, resulting in a PG of 15% for this endpoint. Based on the 1 year results of the ANSWER HDE Study, the anticipated rate for the primary safety endpoint is 7%. Results from a recently published meta-analysis [Fiorella 2017] indicate that the rate of complete occlusion at 1 year of wide-neck bifurcated aneurysms treated with conventional therapies is 46.3% (95% CI: 39.2% - 53.4%) whereas the ANSWER HDE Study described above reports the rate of complete occlusion is 58.8% with the PulseRider® device. With Sponsor's desire to seek strict superiority to a PG of 46.3% for the primary effectiveness endpoint and an expected attrition rate of 10%, one hundred sixty (160) subjects will provide 80% power for the primary safety endpoint and 85% power for the primary effectiveness endpoint.

Statistical Analysis

The primary safety endpoint will be evaluated on all subjects for whom implantation of the PulseRider® device was attempted. Subjects with a missing endpoint will be imputed with a multiple imputation method that will make use of the similarities between the subject's demographic, procedural, and aneurysm characteristics with those of the subjects with a non-missing endpoint. The endpoint will be considered successful if the upper bound of the two-sided 95% confidence interval for its rate is less than a performance goal of 15%.

The primary effectiveness endpoint will be evaluated on all subjects for whom implantation of the PulseRider® device was successful. Subjects with a missing endpoint will be imputed using a multiple imputation method that will make use of the subject's own past

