6.5. Prophylactic Medications, Treatments, and Procedures

Dual anti-platelet medication is required and should be initiated prior to the PulseRider procedure. The antiplatelet and anticoagulation regimen used for interventional intracranial procedures as part of this study is at the discretion of the treating physician. Each center will provide the standard dual anti-platelet therapy regimen followed at their institution to Pulsar Vascular, Inc.

7. Study Schedule

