10.1.6. Analysis Datasets

Modified Intent to Treat Analysis Set

The mITT analysis set consists of all enrolled subjects in whom treatment with the PulseRider device is attempted as defined by advancement of any portion of the PulseRider device outside of the distal end of the microcatheter inside the subject. This includes subjects in which the PulseRider is not fully advanced outside of the microcatheter. It is possible that the PulseRider device may not reach the target aneurysm, and as a result the treating physician does not advance the device outside of the distal end of the microcatheter. In the rare event that this happens, the subject will not be considered part of the mITT population and will instead be followed for 30 days.

Per Protocol (PP) Analysis Set

The PP analysis set consists of all subjects who meet the following criteria:

- there are no major deviations from the protocol eligibility criteria or DAPT requirements
- the subject is successfully implanted with the PulseRider device

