10.3.4. Primary Endpoint Analyses

Primary Safety Endpoint

The primary safety endpoint analysis will be conducted on the mITT analysis set.

If a subject experienced a death due to neurological causes or a major ipsilateral stroke in downstream territory within a year post-procedure then subject will be deemed a failure on the endpoint. If a subject completed the 1 year follow up and did not experience any such event then subject will be deemed a success on the endpoint. If a subject did not complete the 1 year follow up and did not experience such event then the subject will be imputed with a multiple imputation method that will make use of the similarities between the subject's demographic, procedural, and aneurysm characteristics with those of the subjects with a non-missing endpoint (those who either experienced an event and those who completed the study without experiencing an event). The imputation method will also account for the length of time between the procedure and the last time the subject was seen. The longer that time period is, the less likely the subject will be imputed with an event.

Subjects for whom implantation of the PulseRider was attempted but not successful will be followed up to a year. Any safety events which occur due to attempted implant or from retreatment, and which meet the primary safety endpoint definition will count as failures in the analysis. If such a subject is lost to follow-up then subject will be imputed with data based on other subjects for whom the implantation was not successful but who were not lost to follow-up.

The multiple imputation method results in a large collection of imputed datasets. The proportion of primary endpoint events and its variance is computed for each dataset. Within and between imputation variances are then combined according to Rubin's method [Rubin 1996] in order to produce a single variance estimate for the proportion of events.

The endpoint will be considered successful if the upper bound of the 2-sided 95% normal approximation based confidence interval for the rate of events is less than a performance goal of 15%.

Primary Effectiveness Endpoint

The primary effectiveness endpoint analysis will be conducted on the PP analysis set.

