10.3.5. Secondary Endpoint Analyses

The analysis of technical success which is reported by the investigator will be conducted on the mITT analysis set. The endpoint will be considered successful if the lower bound of the 2-sided 95% normal approximation based confidence interval for the rate is greater than a performance goal of 79%.

The analyses of the remaining secondary effectiveness endpoints listed below will be conducted on the PP analysis set using the observed data.

- The ability to retain embolic coils within aneurysm immediately post-procedure as reported by the independent core laboratory
- Complete aneurysm occlusion at 3 years and 5 years as reported by the independent core laboratory
- Adequate aneurysm occlusion at 1 year, at 3 years and 5 years as reported by the independent core laboratory
- The percentage of target aneurysms that are retreated through the 1 year, 3 year and 5 year as reported by the investigator
- The percentage of subjects with significant stenosis defined as > 50% at implant site at 1 year, 3 years and 5 years as reported by the independent core laboratory
- The percentage of subjects with mRS 0-2 at 1 year, 3 years and 5 years

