10.3.10. Sensitivity Analyses

As a sensitivity analysis, the primary safety and effectiveness endpoints will be analyzed as described in section 10.5.4 but without imputing missing endpoint data using the Clopper-Pearson method.

Other sensitivity analyses will analyze the primary endpoints as follows:

- Consider all missing endpoints as successes,
- Consider all missing endpoints as failures,
- A Tipping point analysis which attempts to answer how many subjects with missing primary endpoint data need to change to either successes or failures for success on the endpoint to no longer hold.

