10.3.11. Sub-Group Analyses

Proportions of subjects and 95% confidence intervals of the primary safety and effectiveness endpoints will be presented for the mITT population set with only the observed data and of the primary effectiveness endpoint for the PP population set with only the observed data as appropriate, in the following subgroups:

- sex. Males and Females will also be statistically compared at the 0.1 alpha level using a chi-square test based on a normal distribution.
- race
- ethnicity
- age category (18-35, 36-50, 51-64, 65-75, and 76-80 years)
- aneurysm location - basilar, carotid terminus, MCA and ACOM

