13.2. Study Record Retention and Archiving

The investigator will maintain all essential study documents and source documentation that support the data collected on the study subjects in compliance with FDA guidelines per 21

CFR 812.140(d). Documents must be retained for a period of 2 years after the latter of the following two dates: The date on which the investigation is terminated or completed, or the date that the records are no longer required for purposes of supporting a premarket approval application. The investigator will take measures to ensure that these essential documents are not accidentally damaged or destroyed. If for any reason the investigator withdraws responsibility for maintaining these essential documents, custody must be transferred to an individual who will assume responsibility. Pulsar Vascular, Inc. must receive written notification of this custodial change.

14. Protocol Deviations

The investigator is responsible for ensuring that the clinical investigation is conducted in accordance with the procedures described in the protocol, FDA regulations and any conditions required by the reviewing IRB. A protocol deviation is a failure to comply (intentionally or unintentionally) with the requirements of the clinical study as specified in the protocol. Examples of protocol deviations include late visits, missed visits, required follow-up testing not completed, visit out of window, non-adherence to inclusion/exclusion criteria, etc. and shall be reported to the Sponsor through the eCRFs. Deviations will be reviewed and assessed by the Sponsor.

It is the responsibility of the site to use vigilance to identify and report deviations to the Sponsor and IRB per guidelines. The study monitors shall verify that the conduct of the study is in compliance with the approved protocol and applicable regulations and shall identify deviations and any issues of noncompliance. Corrective and preventative actions will be implemented promptly as necessary and significant protocol deviations that raise subject safety concerns or indicate repeat noncompliance may be grounds for investigator disqualification.

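### The primary effectiveness set is defined two ways, per-protocol membership is not fixed, and no overall analysis counts failed implants as failures

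*Combined protocol and SAP*

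**What the plan says.** The Protocol Summary, under Statistical Analysis, states: "The primary effectiveness endpoint will be evaluated on all subjects for whom implantation of the PulseRider® device was successful". Section 10.3.4 states: "The primary effectiveness endpoint analysis will be conducted on the PP analysis set". Section 10.1.6 gives the per-protocol (PP) set two conditions. One is successful implantation. The other is that "there are no major deviations from the protocol eligibility criteria or DAPT requirements".

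No section defines a major deviation. On antiplatelet treatment, Section 6.5 requires DAPT to be started before the procedure and has each center send its standard regimen to the sponsor, but it also says "The antiplatelet and anticoagulation regimen used for interventional intracranial procedures as part of this study is at the discretion of the treating physician". Section 7.3 carries DAPT past the procedure under institutional standard of care. Section 14 says of deviations in general: "Deviations will be reviewed and assessed by the Sponsor". It gives no rule separating major from minor and no timing relative to outcome data. Section 10 defers further detail to a separate SAP, due for approval before the first data monitoring committee (DMC) data report. That SAP is not among the documents available here.

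Subjects with an attempted but failed implant belong to the mITT set. They count in the safety endpoint (Section 10.3.4) and in technical success: "The analysis of technical success which is reported by the investigator will be conducted on the mITT analysis set" (Section 10.3.5). For effectiveness, Section 10.3.10 varies only how missing endpoints are handled, for example "Consider all missing endpoints as failures". Section 10.3.11 presents effectiveness in mITT by subgroup only, where results "will be presented for the mITT population set with only the observed data". The footnote to Table 7.15A exempts non-implanted subjects from the 1-year DSA.

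**The concern.** Section 10.1.1 makes study success depend on rejecting both primary null hypotheses. The Summary and Section 10.3.4 give the same set only if no implanted subject has a major deviation. Otherwise one trial can produce two conclusions, each supported by current text.

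The PP version is also the more exposed of the two. Because DAPT continues after the procedure, whether a subject deviated may be settled after baseline. This is an open single-arm trial in which investigators grade occlusion themselves (Section 7.8). If deviations are classified once occlusion results are known, the classification could decide the test. That the sponsor would make the call is an inference from Section 14, not something the plan states.

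Separately, either set makes the effectiveness claim conditional on a successful implant. The plan has no overall result showing how far the claim depends on that condition.

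**Working it through.** **Inputs.** Performance goal 46.3% and a two-sided 95% normal-approximation interval (Sections 10.1.1, 10.3.4). Expected complete occlusion 58.8%, 160 subjects, 10% attrition, stated power 85% (Section 10.2). Technical success 34/34 in the earlier HDE study, which covered basilar and carotid terminus aneurysms only (Section 1.3.2). The number of failed implants in this trial is an assumption, because the plan gives none. The examples treat all 160 subjects as attempted and the endpoint as observed.

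**Formula.** Lower bound L = p − 1.96 × √(p(1 − p)/n). The test passes if L > 0.463.

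**The plan's own figure.** n = 160 × 0.9 = 144. The smallest passing count is 79 (78/144 gives L = 0.4603; 79/144 gives L = 0.4673). The exact binomial probability of at least 79 of 144 at p = 0.588 is 0.852. The stated 85% reproduces.

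**Conflict between the two sets.**

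| Result | p | L | Outcome |
|---|---|---|---|
| 77/144, all implanted (Summary) | 0.5347 | 0.4533 | fails |
| 77/141, three non-occluded subjects excluded (Section 10.3.4) | 0.5461 | 0.4639 | passes |
| 78/144, all implanted | 0.5417 | 0.4603 | fails |
| 78/143, one non-occluded subject excluded | 0.5455 | 0.4638 | passes |

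Near the boundary, one classification is enough.

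**Failed implants counted as failures.**

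| Implanted only | L | All attempted | L |
|---|---|---|---|
| 79/144 = 54.9% | 0.4673, passes | 79/160 = 49.4% (16 failed) | 0.4163, below goal |
| 83/152 = 54.6% | 0.4669, passes | 83/160 = 51.9% (8 failed) | 0.4413, below goal |
| 85/144 = 59.0% (about the planned rate) | 0.5100, passes | 85/158 = 53.8% (14 failed) | 0.4602, below goal |
| 92/156 = 59.0% (about the planned rate) | 0.5126, passes | 92/160 = 57.5% (4 failed) | 0.4984, above goal |

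For 85/144, fourteen is the smallest number of added failures that takes L below the goal; thirteen gives 85/157, L = 0.4635.

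**How many failures are plausible.** For 0 of 34, the exact 95% upper limit is 1 − 0.025^(1/34) = 0.103. The HDE data are therefore compatible with up to about 10% failed implants, and they include no MCA or ACOM aneurysms. Technical success itself can pass with 15% failures: 136/160 = 85% has L = 0.7947, above its 79% goal.

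**Whether the planned analyses fill the gap.** Failed implants lie outside the PP set, so treating missing endpoints as failures within the primary analysis does not reach them. The mITT subgroup results use observed data, and non-implanted subjects need no 1-year DSA, so most would drop out there too. Technical success counts them, but as a separate endpoint.

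**The case against.** The strongest reply is that the body of the protocol is consistent. Sections 10.3.4, 10.3.11 and 10.3.12 all use PP for this endpoint, so the Summary may be shorthand and correcting one sentence would reconcile the text. That would remove the contradiction. It would also leave study success resting on the version whose membership is undefined, and this is why aligning on the Summary's set is preferable.

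Second, the separate SAP may define major deviations before any DMC data report. That is possible, and the point about membership is limited to the documents available. A definition there would still leave the protocol naming two primary sets.

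Third, the examples are chosen near the boundary. This is fair. At the planned 58.8%, observing exactly 77 or 78 of 144 has a probability of about 6%. If three exclusions were unrelated to outcome, all three would be non-occluded about 10% of the time (67/144 × 66/143 × 65/142 = 0.098). With one occluded subject among the three, 76/141 has L = 0.4567 and still fails. Sixteen failures in 160 is close to the upper limit from the HDE data, and twelve at the planned rate would still clear the goal (87/160, L = 0.4666). The planned analysis also uses multiple imputation, so a plain interval on 144 is an approximation. The examples show that the choice of set can decide the result, not that it probably will.

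Fourth, conditioning on implantation is a legitimate choice of estimand, and failed implants are reported openly under safety and technical success. That stands as a reason not to change the primary set to mITT. It does not replace an overall effectiveness result that counts them.

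**Conclusion.** The concern holds and should be fixed. The Summary and Section 10.3.4 define different primary effectiveness sets. The available text does not fix PP membership, and no planned overall analysis scores failed implants as effectiveness failures. Near the boundary, one to three deviation calls can reverse the study conclusion.

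The effect of failed implants depends on an assumed failure rate. It is small at 4 of 160. At 16 of 160, a just-passing 54.9% becomes 49.4% of attempted subjects, with a lower bound of 41.6%. These figures describe a difference in what is being estimated; they do not show an inflated type I error for the stated test. The sample-size statement for effectiveness is correct on its own inputs.

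**What to change.** 1. State in both the Summary and Section 10.3.4 that the primary effectiveness set is all successfully implanted subjects, with no exclusion for deviations.
2. Keep PP as a supportive set. In Section 10.1.6, define a major deviation and say who fixes PP membership. Require this to be done before any core laboratory outcome is reviewed.
3. Add to Section 10.3.10 a named overall mITT analysis that counts every attempted but not implanted subject as a failure and imputes missing implanted subjects as in Section 10.3.4. Label it a sensitivity analysis: Section 10.1.1 describes the source of the 46.3% goal as studies with follow-up imaging and does not say how they treated abandoned procedures.
4. Make conforming edits in Sections 10.3.11 and 10.3.12, which also name PP for this endpoint.

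The cost is wording and one extra analysis of data already collected. The downside is that the mITT rate will be somewhat lower than the primary rate if any implants fail.

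Making mITT the primary set is not requested. With the success rate taken as 0.588 × the implant success rate, exact power at n = 144 would fall from 85.2% to 77.5% with 2% failed implants and to 62.9% with 5%.

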10.1.5. Levels of Significance

A 2-sided alpha of 0.05 will be used for statistical testing and confidence intervals unless otherwise noted. There will be no adjustment of significance levels or p-values for testing multiple hypotheses. Both primary endpoints must be met for study success and the secondary effectiveness endpoint of technical success will only be tested if the primary endpoints are met.

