Success on this endpoint is defined as complete aneurysm occlusion (Raymond I) without retreatment or significant parent artery stenosis (> 50% stenosis) at 1 year post-procedure. If the 1 year imaging is not available and if the subject did not experience a retreatment then the subject will be imputed using an imputation method that will make use of the subject's own past occlusion and stenosis evaluations if available and the similarities between the subject's demographic, procedural, and aneurysm characteristics with those of the subjects with a non-missing endpoint.

The multiple imputation method results in a large collection of imputed datasets. The proportion of complete aneurysm occlusion and its variance is computed for each dataset. Within and between imputation variances are then combined according to Rubin's method in order to produce a single variance estimate for the proportion of complete aneurysm occlusion.

The endpoint will be considered successful if the lower bound of the 2-sided 95% normal approximation based confidence interval for the rate is greater than a performance goal of 46.3%.

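### The primary effectiveness test covers only successfully implanted subjects, and no planned overall analysis of that endpoint counts a failed implant as a failure

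*Combined protocol and SAP*

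**What the plan says.** - Section 10.3.4 fixes the population for the primary effectiveness test: "The primary effectiveness endpoint analysis will be conducted on the PP analysis set".
- Section 10.1.6 gives two conditions for PP: "there are no major deviations from the protocol eligibility criteria or DAPT requirements" and "the subject is successfully implanted with the PulseRider device".
- The Protocol Summary (Statistical Analysis) names only the implantation condition: "The primary effectiveness endpoint will be evaluated on all subjects for whom implantation of the PulseRider® device was successful".
- Safety uses a wider set. Section 10.1.6 says: "The mITT analysis set consists of all enrolled subjects in whom treatment with the PulseRider device is attempted". Section 10.3.4 follows attempted but unsuccessful implants for a year and counts their events.
- The effectiveness rule in 10.3.4 is that the lower bound of the two-sided 95% "normal approximation based confidence interval for the rate is greater than a performance goal of 46.3"%.
- Section 10.3.10 repeats the primary analyses with different treatment of missing endpoints, for example "Consider all missing endpoints as failures". It points to a section 10.5.4 that does not exist; 10.3.4 appears to be meant.
- Section 10.3.11 shows effectiveness on mITT only within subgroups and on observed data. The footnotes to the schedule of assessments exempt non-implanted subjects from the 1-year DSA.
- Technical success is a secondary effectiveness endpoint, analysed on mITT against 79% (10.1.2, 10.3.5). It is tested only after both primary endpoints are met (10.1.5), and study success rests on the two primary endpoints alone (10.1.1).

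**The concern.** Whether an implant succeeds is learned during treatment, so selecting on it removes subjects for whom the device did not work. A failed implant lies outside PP. It is therefore never a missing PP endpoint, and even the analysis that treats all missing endpoints as failures does not reach it. Most failed implants would also be absent from the observed-data mITT subgroup rows, because no 1-year DSA is required of them.

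Risk is thus judged on the mITT set and benefit on the part of it in which implantation worked. According to section 2.1 the data are to support a premarket approval application. A reader of the effectiveness result would want to know whether it also holds for patients in whom the device is tried, and the plan as written does not produce that figure.

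**Working it through.** **Inputs from the documents.** 160 subjects; 10% attrition; expected complete occlusion 58.8%; goal 46.3% (10.2). Level, from 10.1.5: "A 2-sided alpha of 0.05 will be used for statistical testing and confidence intervals unless otherwise noted". The goal of 46.3% is taken from the decision criterion; the null hypothesis line in 10.1.1 prints 46.34%. Technical success goal 79%, with at least 85% needed at 160 subjects (10.1.2). Earlier study: 34/34 implanted (1.3.2).

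**Formula.** With x successes in n and p = x/n, the lower bound is L = p − 1.96 × √(p(1 − p)/n). The rule passes if L > 46.3%.

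**Step 1: the plan's own figure.** n = 160 × 0.9 = 144. The smallest passing count is 79 (79/144 = 54.86%, L = 46.73%; 78/144 gives L = 46.03%). The binomial probability of at least 79 of 144 at 58.8% is 85.2%, which reproduces the stated 85% power.

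**Step 2: one count, two denominators.** Assume 160 attempted, complete data and no other PP exclusions. Take the smallest count that passes among implanted subjects and divide it by 160. Example: 84/160 = 0.525; √(0.525 × 0.475/160) = 0.0395; L = 0.525 − 1.96 × 0.0395 = 44.8%.

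| Failed implants | Among implanted | L | Over all attempted | L |
|---|---|---|---|---|
| 0 | 87/160 = 54.4% | 46.66% | 87/160 = 54.4% | 46.66% |
| 1 | 86/159 = 54.1% | 46.34% | 86/160 = 53.75% | 46.02% |
| 5 | 84/155 = 54.2% | 46.35% | 84/160 = 52.5% | 44.76% |
| 16 | 79/144 = 54.9% | 46.73% | 79/160 = 49.4% | 41.63% |
| 24 | 75/136 = 55.1% | 46.79% | 75/160 = 46.9% | 39.14% |
| 25 | 74/135 = 54.8% | 46.42% | 74/160 = 46.25% | 38.52% |

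At the threshold, one failed implant changes the decision. The all-attempted point estimate falls below 46.3% only from 25 failures.

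**Step 3: which failure rates are plausible.** The documents give no expected rate for this trial. Zero failures in 34 has an exact two-sided 95% upper limit of 1 − 0.025^(1/34) = 10.3%. The technical success goal sets a looser bound: 136/160 = 85% has L = 79.5% and passes, while 135/160 has L = 78.75% and fails. So 24 failures (15%) is an extreme case that lies outside the earlier study's limit.

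**Step 4: how often the two could part.** Suppose the true rate over all attempted subjects is exactly 46.3% and a share s of implants succeeds. The rate among implanted subjects is then 46.3%/s. With the number implanted binomial (160, s), the implanted-only rule is met with these probabilities:

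| s | Rate among implanted | Probability |
|---|---|---|
| 100% | 46.3% | 2.5% |
| 97% | 47.7% | 5.8% |
| 95% | 48.7% | 9.3% |
| 90% | 51.4% | 24.4% |

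**The case against.** The strongest reply is that the choice is open and the failures are not hidden. Conditioning on implantation is stated in the Protocol Summary, 10.1.6 and 10.3.4. Failed implants count against technical success on mITT and remain in the safety analysis. The only implant evidence in the documents is 34/34, and if that is repeated the two denominators coincide. Section 10 also announces a separate, more detailed SAP.

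Much of this stands, and it rules out several stronger readings that a reader might infer:

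- *No planned analysis counts a failed implant as a failure.* Technical success does. The gap concerns the occlusion endpoint.
- *The device could succeed with an all-attempted rate below 46.3%.* In the cases with up to 24 failures the rate stays above 46.3% and only the lower bound falls short. At the planned 58.8% among implanted subjects, the true all-attempted rate reaches 46.3% only if 1 − 46.3/58.8 = 21.3% of implants fail.
- *The type I error is inflated.* The probabilities in Step 4 are not error rates of the stated test. When the rate among implanted subjects is 51.4%, rejecting 46.3% is correct for the declared population. The figures show the distance between two estimands.
- *The 46.3% is itself an all-attempted rate.* The documents do not say how the source meta-analysis handled failed attempts. Section 10.1.1 describes outcomes with at least one follow-up image.

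The reply does not supply the missing analysis. Disclosure does not produce an all-attempted estimate, and a promised SAP does not specify one. The 34/34 comes from basilar and carotid terminus aneurysms only, whereas this trial adds MCA and ACOM.

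**Conclusion.** The concern holds in a limited form. The primary effectiveness test conditions on a result of treatment, and no planned overall analysis of that endpoint shows what happens when failed implants are counted. The lower-bound rule can be met among implanted subjects and missed over all attempted subjects, at the threshold after a single failed implant and by a wider margin as failures accumulate.

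The practical size runs from nil at the earlier study's rate to a lower bound of 41.6% instead of 46.7% at 16 failures. The 24-failure case is an outer bound. These figures assume 160 attempted subjects, complete data and no other PP exclusions; the range of failure rates is an assumption. Attempted is meant in the mITT sense, which leaves out subjects in whom no part of the device left the microcatheter. This is a gap in supportive analysis and labelling. It does not make the stated test invalid for its declared population.

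**What to change.** Keep the primary test and sample size. Add to 10.3.10 a supportive analysis of the primary effectiveness endpoint on the mITT set. Score each failed implant as a failure, which needs no 1-year DSA, handle other missing data as in 10.3.4, and use the same interval with 46.3% as the reference. Report it beside the PP result wherever effectiveness is claimed, and describe the PP result as applying to subjects successfully implanted without major eligibility or DAPT deviations.

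Two cautions belong in the text. Moving to mITT also restores subjects with major eligibility or DAPT deviations, so a difference from PP will not be due to failed implants alone. The comparison with 46.3% should carry the note that the source's handling of failed attempts is not stated.

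The cost is one sentence and one extra analysis on data already collected, and a somewhat lower reported rate. The analysis should stay supportive, because the trial was not sized for it. With 160 attempted, complete data and 58.8% among implanted subjects, its lower bound would exceed 46.3% with probability about 78%, 68% and 39% at 97%, 95% and 90% implant success, against about 89%, 88% and 86% for the implanted-only rule.
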